Medical and scientific judgment should be exercised in deciding whether expedited reporting is appropriate in other situations, such as IMEs that may not be immediately life-threatening or result in death or hospitalization but may jeopardize the health of the subject or may require intervention to prevent one of the other outcomes listed in the definition above. These IMEs should also usually be considered serious. Examples of such events include allergic bronchospasm requiring intensive treatment in an emergency room or at home, blood dyscrasias or convulsions that do not result in inpatient hospitalization, or the development of drug dependency or drug abuse, new onset diabetes, or autoimmune disease.

Adverse Reaction:

All noxious and unintended responses to a medicinal product related to any dose should be considered adverse reactions (AR).

(The phrase “responses to a medicinal product” means that a causal relationship between a medicinal product and an AE is at least a reasonable possibility)

The following additional definitions are used by Sanofi Pasteur:

Immediate Event/Reaction:

Immediate events are recorded to capture medically relevant unsolicited systemic AEs (including those related to the product administered) that occur within the first 30 minutes after vaccination.

Solicited Reaction:

A solicited reaction is an “expected” adverse reaction (sign or symptom) observed and reported under the conditions (nature and onset) pre-listed in the protocol and CRB (eg, injection site pain or headache occurring between D0 and D7 post-vaccination).

By definition, solicited reactions are to be considered as being related to the product administered.

For injectable vaccines, solicited reactions can either be solicited injection site reactions or solicited systemic reactions.

Unsolicited AE / AR:

^a The term “life-threatening” refers to an event in which the subject was at risk of death at the time of the event; it does not refer to an event which hypothetically might have caused death if it were more severe.

^b All medical events leading to hospitalizations will be recorded and reported as SAEs, with the exception of: hospitalization planned before inclusion into the study or outpatient treatment with no hospitalization.

^c “Persistent or significant disability or incapacity” means that there is a substantial disruption of a person’s ability to carry out normal life functions.

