- To describe in each vaccine group the use of antibiotics and antivirals that are associated with any ILI, within 30 days after the onset of the ILI
- To describe in each vaccine group hospitalizations that are associated with cases of laboratory-confirmed ILI, within 30 days after onset of the ILI
- To describe in each vaccine group hospitalizations that are associated with any ILI, within 30 days after onset of the ILI
- To describe in each vaccine group emergency room visits that are associated with cases of laboratory-confirmed ILI, within 30 days after onset of the ILI
- To describe in each vaccine group emergency room visits that are associated with any ILI, within 30 days after onset of the ILI
- To describe in each vaccine group non-routine medical office visits (including urgent care visits) that are associated with cases of laboratory-confirmed ILI, within 30 days after onset of the ILI

- To describe in each vaccine group non-routine medical office visits (including urgent care visits) that are associated with any ILI, within 30 days after onset of the ILI
- To describe in each vaccine group medication use that is associated with cases of laboratory-confirmed ILI, within 30 days after onset of the ILI
- To describe in each vaccine group medication use that is associated with any ILI, within 30 days after onset of the ILI
- To describe in each vaccine group absenteeism (Parent(s) / guardian's absenteeism due to child sick days) that is associated with cases of laboratory-confirmed ILI, within 30 days after onset of the ILI
- To describe in each vaccine group absenteeism (Parent(s) / guardian's absenteeism due to child sick days) that is associated with any ILI, within 30 days after onset of the ILI

Correlates of protection objective

To assess the association of HAI titers to the 4 vaccine strains with the occurrence of laboratory-confirmed ILI of any influenza A or B type, or of viral strains similar to those contained in the vaccine.

Antibody persistence

To describe the persistence of immune response 1 year after vaccination among subjects from Season 1 (NH) who are re-enrolled for Season 3 (NH) according to the vaccine received in Season 1 (NH).

3 Description of the Overall Study Design and Plan

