3.2 Study Plan

The study plan is summarized in the Table of Study Procedures ([Table 3.1](#), [Table 3.2](#), [Table 3.3](#), [Table 3.4](#), [Table 3.5](#), [Table 3.6](#), and [Table 3.7](#)).

The study will span several influenza seasons in different countries. Subjects may receive 1 or 2 vaccinations, depending on previous influenza vaccination history, and may provide blood draws according to the protocol-defined objectives.

Vaccination

For the Sentinel Safety Cohort, eligible subjects will receive QIV-HD with no comparator vaccine as follows:

- Subjects who were previously vaccinated against influenza will receive 1 dose of the QIV-HD on Day (D) 0.
- Subjects who have not previously been vaccinated against influenza will receive 2 doses of QIV-HD. Each dose will be administered 28 days apart (at D0 and D28).

For all other eligible subjects in the study who are not part of the sentinel safety cohort, these subjects will be randomized to receive either QIV-HD or QIV-SD:

- Subjects who were previously vaccinated against influenza will receive 1 dose of QIV-HD or QIV-SD on D0.
- Subjects who had not previously been vaccinated against influenza will receive 2 doses of QIV-HD or QIV-SD. Each dose will be administered 28 days apart (at D0 and D28).

An unblinded administrator at each site will administer the vaccine.

Surveillance for influenza-like illness (not applicable for Sentinel Safety Cohort or Re-vaccination Cohort):

Passive Surveillance: Following randomization and vaccinations, all subjects' parents / guardians (except those in the Sentinel Safety Cohort or the Re-vaccination Cohort) will be instructed to contact the site if the subject experiences symptoms of a protocol-defined ILI during the annual

surveillance periods, from the 1st vaccination (D0) until 30 April of the following year for subjects in the NH or until 31 October of the same year for subjects in the SH.

Active Surveillance: During a period from the 1st vaccination (D0) until approximately 30 April for NH seasons or 31 October for SH seasons, subjects' parents/guardians will be contacted by telephone once a week.

Collection of nasopharyngeal (NP) swabs

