4.4.3 Efficacy

For each subject, the efficacy endpoints will be derived based on a combination of the following items:

ILI occurrence: at each ILI visit, the occurrence of a temperature of $\geq 100.4^{\circ}\text{F}$ (38°C), starting more than 14 days after the 1st vaccination for the Full Analysis Set for Efficacy (FASE) as defined in [Section 5.2.1](#) and last vaccination for the Per-Protocol Analysis Set for Efficacy (PPASE) as defined in [Section 5.2.2](#) and concurrent with at least one other symptom meeting the definition of an ILI¹ will be considered as an ILI occurrence.

Notes:

- The start date of the ILI is the start of fever $\geq 100.4^{\circ}\text{F}$ (38°C)
- Start and end dates of fever are considered as the start and end date of the ILI (when the end date is unknown, the last date the fever is known to be present is used)
- The date of start / end of each symptom is used in comparison of start and end of fever $\geq 100.4^{\circ}\text{F}$ (38°C) to define concurrent symptoms with ILI: when start and end dates for fever and one other protocol-defined symptom are not missing, the start date for fever is \leq the end date for the symptom and the end date for fever is \geq the start date for the symptom

¹ Cough, wheezing, difficulty breathing, nasal congestion, rhinorrhea, pharyngitis (sore throat), otitis, vomiting, diarrhea, shivering, fatigue, headache or myalgia

- After the end of an ILI episode, an interval of 2 days has to pass before a new ILI episode can be considered
- For the primary and secondary objectives, in case of more than one occurrence of the same efficacy endpoint for the same subject, only the first occurrence based on the start date of the fever ($\geq 100.4^{\circ}\text{F}$ [38°C]) is considered for the estimation of vaccine efficacy for the prevention of this endpoint

Modified CDC-defined ILI is the occurrence of a temperature of $\geq 100.4^{\circ}\text{F}$ (38°C), starting more than 14 days after the first vaccination and concurrent with cough or pharyngitis (sore throat). The same derivation rules for ILI occurrence will be used.

PCR-confirmed influenza case: An ILI occurrence is PCR-confirmed as positive for influenza A or B types if the PCR result of the corresponding NP swab, recorded at the corresponding ILI visit in the database and taken within 10 days after the start of the ILI, is positive for influenza.

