5.1.3.2 ILI-associated with events and healthcare utilization

Events and healthcare utilization associated with cases of laboratory-confirmed influenza ILI caused by any viral type / subtype and with any ILI occurring within 30 days after the ILI onset will be presented for each vaccine group with statistics presented on [Table 5.1](#).

5.1.3.3

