5.2.9 Populations Used in Analyses

The primary and secondary efficacy analyses with hypotheses tests will be performed on the PPASE and all the efficacy analyses will be performed on the FASE. The PPASE will be the main analysis set for the non-inferior efficacy analysis and the FASE will be the main analysis for all the superior efficacy analyses.

The secondary immunogenicity analysis for superiority testing will be performed on the FASI and will be confirmed on the PPASI. The secondary analyses for the immunogenicity descriptive assessment will be performed on the IAS.

The analyses of efficacy endpoints for observational objectives and ILI-associated symptoms / events will be performed on the FASE. Analyses of antibody persistence and re-vaccination response will be performed on a subset of IAS enrolled in Seasons 1 and 3 and with blood samples drawn in both seasons.

In addition to the ones above, other analysis sets will be taken into account in the description of the population (eg, the disposition, the demographic, or baseline characteristics).

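### In two-dose children, fever with a listed symptom in the week after dose 2 can count as any ILI, so the descriptive any-ILI tables can mix vaccine reactions with illness

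*SAP*

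**What the plan says.** Among the observational objectives in SAP 2.3 is this one: "To describe in each vaccine group medication use that is associated with any ILI, within 30 days after onset of the ILI". Parallel objectives cover ILI symptoms, visits and absenteeism.

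SAP 4.4.3 counts an ILI in the FASE when a fever of at least 38 °C occurs "starting more than 14 days after the 1st vaccination for the Full Analysis Set for Efficacy (FASE"), and "concurrent with at least one other symptom meeting the definition of" an ILI. The qualifying symptoms end with "otitis, vomiting, diarrhea, shivering, fatigue, headache or myalgia". For the per-protocol set (PPASE) the 14 days run from the last dose instead.

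SAP 5.2.9 fixes the population: "The analyses of efficacy endpoints for observational objectives and ILI-associated symptoms / events will be performed on the FASE". SAP 5.1.3.2 tabulates events and healthcare use linked to laboratory-confirmed ILI "and with any ILI occurring within 30 days after the ILI onset will be presented for each vaccine group". SAP 4.4.4.4 makes the link by date only: an event belongs to an ILI if it starts 0 to 30 days after fever onset.

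On vaccination of previously unvaccinated children, SAP 3.2 says "Each dose will be administered 28 days apart (at D0 and D28"); the visit schedule adds a window of +7 days.

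On safety, protocol Table 9.3 lists fever of at least 38.0 °C and vomiting among the solicited systemic reactions for days 0 to 7 after each vaccination. Protocol 9.3.3.2 adds: "By definition, solicited reactions are to be considered as being related to the product administered". SAP 5.3.3.2 takes the same position.

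**The concern.** The 14-day rule keeps reactions to dose 1 out of the FASE illness counts, but nothing does the same for dose 2. A two-dose child who has fever and vomiting the day after dose 2 satisfies the date and symptom rules for an ILI. Where solicited reactions are collected (all of Season 1, and the ESafAS in Seasons 2 and 3), the same episode is also tabulated as a reaction to the vaccine. No text says how an episode that is both should be handled.

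The any-ILI tables are meant to describe illness and its burden by vaccine: symptoms, visits, parental absence and medication. If they include dose-2 reactions, a real difference in illness is pulled towards no difference. If systemic reactogenicity differed between the vaccines, part of that difference would also be read as illness.

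**Working it through.** The plan gives no figure on this point, so there is none to reproduce. The check has two parts: dates from the documents, then size on assumed rates.

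**Dates.**
- Dose 2 is given on day 28 to 35 after dose 1 (protocol 5.1.4.3). The per-protocol rule extends to day 38 (SAP 5.2.2).
- The reaction period is days 0 to 7 after each dose (protocol 9.3.3.3.2).
- Reaction days after dose 2, counted from dose 1: 28 + 0 = 28 to 35 + 7 = 42, or 38 + 7 = 45 with the longer window.
- FASE cutoff (more than 14 days after dose 1): all 8 × 8 = 64 combinations of dose-2 day and reaction day count, or 11 × 8 = 88 of 88 with the longer window.
- PPASE cutoff (more than 14 days after the last dose): 0 of 64 and 0 of 88.
- Week after dose 1 under the FASE cutoff: 0 of 8 days count.

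**Symptoms.** Fever has the same threshold on both lists, but fever alone is not an ILI. Of the other solicited systemic terms, vomiting is the only one that is literally an ILI symptom. Drowsiness resembles fatigue but is a separate CRF term (protocol Tables 9.1 and 9.3). A coincident cough or runny nose would also complete the definition.

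**Share of any-ILI episodes.** Let p be the share of children given two doses, r the proportion of them with a qualifying fever plus symptom as a reaction to dose 2, and b the other ILIs per child. None of the three is in the documents. Share = p·r / (p·r + b).

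| Assumed ranges | Lowest | Highest |
|---|---|---|
| p 0.5-1.0, r 0.005-0.05, b 0.5-1.5 | 0.0025/1.5025 = 0.2% | 0.05/0.55 = 9.1% |
| p 0.5-0.8, r 0.03-0.08, b 0.5-1.0 | 0.015/1.015 = 1.5% | 0.064/0.564 = 11.3% |

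**Comparison between arms.** With no true difference in illness, the QIV-HD/QIV-SD ratio of ILIs per child is (b + p·r_HD) / (b + p·r_SD).
- Equal reaction rates: 1.00.
- Assumed rates of 5% (QIV-HD) and 3% (QIV-SD): from (1.5 + 0.025)/(1.5 + 0.015) = 1.007 (p = 0.5, b = 1.5) to (0.5 + 0.05)/(0.5 + 0.03) = 1.038 (p = 1, b = 0.5).

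Dilution at equal reaction rates, for an assumed true ratio of 0.80 with p = 1, r = 0.05 and b = 0.5: (0.40 + 0.05)/(0.50 + 0.05) = 0.82.

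**What a date rule would set aside.** For a child enrolled on 1 October 2022, 211 days run to 30 April 2023, of which 211 − 14 = 197 count. Eight days are 8/197 = 4.1% of that time. Starting on 15 September or 1 November gives 8/213 = 3.8% or 8/166 = 4.8%.

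**The case against.** The strongest reply is that a clinician stands between the fever and the table. The SAP derives an ILI at an ILI visit, where a blinded investigator confirms the diagnosis clinically (protocol 5.1.5.1). A swab also requires symptoms that last, or come back after, at least 12 hours (protocol 5.1.3). This will remove some reactions. It does not close the gap, because the investigator has no instruction about vaccine reactions and the SAP derivation uses only dates and symptoms.

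A second reply is that any ILI is syndromic by intent, that counting from the first dose suits a full analysis set, and that laboratory-confirmed counterparts are already planned. That is a good reason to keep the planned tables, though it does not tell a reader how much of them is dose-2 reaction.

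Three stronger readings are tempting:
- A reader might infer that all antipyretic use after dose 2 enters the ILI medication table. Protocol 6.6 records medication given for an adverse event only under the action-taken item of the AE form, while ILI visits collect medication separately. The documents do not say which applies when an episode is both, so that component is uncertain.
- A reader might infer that the tables are biased against QIV-HD. The only evidence in the documents is the Phase II finding of similar systemic reactogenicity. That study was limited in size, so a difference is possible but not shown.
- A reader might infer that the efficacy result is affected. The primary and confirmatory efficacy endpoints require a positive PCR or culture, which a vaccine reaction does not supply.

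**Conclusion.** The point holds as a gap in the definition of descriptive tables. In two-dose children, fever with a concurrent listed symptom starting on days 0-7 after dose 2 passes the FASE date and symptom rules for any ILI, although protocol and SAP class the fever and vomiting as vaccine-related wherever solicited reactions are collected. ILI symptoms, visits and absenteeism can be affected, and medication use possibly.

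The overlap in dates is certain. The size is not: the range of roughly 0.2% to 11% of ILIs rests entirely on assumed two-dose shares, reaction rates and background ILI rates, and takes no account of episodes screened out at the ILI visit. Dilution is the main expected effect. Children who receive one dose are not affected, and no confirmatory conclusion depends on this.

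**What to change.** In SAP 4.4.4.4, add a flag for every ILI whose fever starts on days 0-7 after dose 2. In SAP 5.1.3.2, keep the any-ILI tables as planned and add, by vaccine group, a row for the flagged ILIs and the any-ILI results without them. Leave the laboratory-confirmed endpoints unchanged, and settle the rule before unblinding.

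The flag should use dates alone. Restricting it to episodes without laboratory confirmation would make the count depend on a post-randomization test, and would also set aside true influenza that was never swabbed. The dose-2 date exists for every two-dose child, so the flag works outside the ESafAS too.

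The cost is one derived variable and some extra rows, with no new data collection. The results without flagged ILIs will omit true illnesses that begin in those 8 days, about 4% to 5% of the counting period in the examples above; the planned table still includes them.

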3.1 Study Design

QHD00014 is planned to be a Phase III, randomized, modified double-blind, active-controlled, multi-center study to be conducted in 13,320 (100 subjects will be in an open-label Sentinel Safety Cohort with no comparator vaccine while 13,220 will be randomized and double-blinded) children 6 months through 35 months of age to evaluate the relative efficacy, immunogenicity, and safety of QIV-HD administered by intramuscular (IM) route versus a QIV-SD vaccine.

QHD00014 is planned to be conducted during the 2020-2021 NH influenza season (Sentinel Safety Cohort), the 2021-2022 NH influenza season (Season 1), the 2021 Southern Hemisphere (SH) influenza season (Season 2), and the 2021-2022 NH influenza season (Season 3). During Seasons 1 through 3, subjects will be randomized in a 1:1 ratio to receive either QIV-HD or QIV-SD prior to the start of the influenza season. Subjects will receive either 1 or 2 doses of study vaccine depending on whether they were previously vaccinated against influenza or previously unvaccinated against influenza, respectively.

During the 2020-2021 NH influenza season, a Sentinel Safety Cohort of 100 US subjects will be enrolled in an uncontrolled, open-label design without a comparator vaccine to evaluate the safety of QIV-HD prior to the enrollment of additional subjects. These subjects will not provide blood samples and will not be followed for ILI surveillance. Following the enrollment of the Sentinel Safety Cohort and prior to the start of Season 1 (2020-2022 NH), an Independent Data Monitoring

Committee (IDMC) will review the safety of this sentinel cohort. If the IDMC determines there is no significant safety issue during their review of the Sentinel Safety Cohort's data, approximately [REDACTED] subjects will subsequently be allowed to be enrolled in Season 1.

The sample size in the subsequent seasons may be adjusted to maintain the likelihood of achieving the overall expected number of cases for the primary endpoint. The current estimated sample size for the efficacy cohort in Seasons 2 and 3 is [REDACTED] subjects [REDACTED] and an additional [REDACTED] subjects from Season 1's Immunogenicity Subset will be re-enrolled in Season 3 but will not be included in efficacy analysis for Season 3, for a total of 13,320 subjects in the entire study. Sentinel Safety Cohort subjects will be excluded from re-enrollment in any subsequent seasons.

During each influenza season, a subset of subjects (hereafter referred to as the Immunogenicity Subset) will be randomly selected using Interactive Response Technology (IRT) across participating sites to provide blood samples for immunogenicity testing:

- Total subjects with blood draws = approximately [REDACTED] subjects
- Season 1, NH = [REDACTED] subjects
- Season 2, SH = [REDACTED] of randomized subjects (approximately [REDACTED] subjects)
- Season 3, NH = [REDACTED] of randomized subjects (approximately [REDACTED] subjects) and [REDACTED] re-enrolled subjects who were part of Season 1*

An ESafAS will also be selected for collection of reactogenicity and unsolicited adverse events as follows:

- Total subjects in ESafAS = [REDACTED] subjects
- Sentinel Safety Cohort (2020-2021 NH) = 100 subjects[†]
- Season 1, NH = [REDACTED] subjects (all subjects)[†]
- Season 2, SH = [REDACTED] of randomized subjects (approximately [REDACTED] subjects)
- Season 3, NH = [REDACTED] of randomized subjects (approximately [REDACTED] subjects) and [REDACTED] re-enrolled subjects from Season 1

*A subset of approximately [REDACTED] subjects from Season 1 (2021-2022 NH) who are in the Immunogenicity Subset will be re-enrolled and re-randomized in Season 3 (hereafter referred as the Re-vaccination Cohort) and included in the ESafAS and the Immunogenicity Subset; these [REDACTED] subjects will not be followed for ILI surveillance during their participation in Season 3.

[†]Note: For the Sentinel Safety Cohort season and Season 1: all enrolled subjects will be included in the ESafAS.

For Seasons 2 and 3: the Immunogenicity Subset and the ESafAS will include the same subjects.

Following the end of Season 2, if the likelihood of achieving the expected [REDACTED] influenza cases at the end of the Season 3 is low an extension of the study to a 4th season may be considered, and if at least [REDACTED] evaluable influenza cases meeting the primary endpoint have occurred, an interim analysis of the efficacy of QIV-HD relative to QIV-SD for the primary efficacy endpoint is planned to be conducted by an independent statistician and reviewed by an IDMC during Season 3. The IDMC may recommend stopping the study at the end of Season 3 without adding any additional study seasons if the primary objective and first secondary objectives are demonstrated,

if there is a high probability to demonstrate these objectives at the end of the ongoing season, or for futility if the probability to demonstrate the primary objective at the end of the study is too low.

Due to the unpredictable epidemiology of influenza, the sample size and / or the duration of the study may be adjusted based on the total number of influenza cases, blinded so that the Sponsor does not know which study vaccine each subject received, in order to maintain the likelihood of achieving the expected number of influenza cases for the primary endpoint.

